5.2 Masking and Unmasking

An independent biostatistician who is not otherwise involved in the trial will generate the complete randomized study drug kit list. Subjects, Investigators and Ora/SDC staff will be masked during the randomization process and throughout the study.

With each shipment of study drug, sites will receive one emergency unmasking envelope for every study drug kit received. The envelopes and kits will both be labeled with the same 4-digit study drug kit number. The envelopes are sealed and contain the unmasked treatment information for the corresponding study drug kit. Envelopes should be stored in a secured location.

Under normal circumstances, the mask should not be broken. When medically necessary, an investigator may need to determine what treatment has been assigned to a subject. The investigator will contact Noveome Biotherapeutics, Inc. with the details of the emergency unmasking request. Noveome Biotherapeutics, Inc. will make the final determination if the unmasking request will be granted. If

granted, the investigator will be permitted to use the code-break instructions available on site. If the investigator determines that emergency unmasking is necessary, the investigator should identify and retrieve the emergency unmasking envelope for the given subject. The emergency unmasking envelope should be opened by the designated site personnel. The investigator must also indicate in source documents and in the eCRF that the mask was broken and provide the date, time, and reason for breaking the mask. Subjects should have their study drug discontinued immediately if treatment assignment is unmasked.

The overall randomization code will be broken only for reporting purposes. This will occur once all final clinical data have been entered into the database, data queries have been resolved, and assignment of subjects to the analysis populations has been completed. The database will be kept masked until after the database lock has occurred.

6. Sample Size and Power Considerations

This Phase 2 study, designed to evaluate the safety and effectiveness of ST266 for the treatment of allergic conjunctivitis, is exploratory in nature. Given there are no data available on which to base a formal power calculation, a sample size of [REDACTED] subjects per group has been selected based on the Investigators' judgment and experience conducting similar Phase 2 studies of this nature in individuals diagnosed with allergic conjunctivitis.

7. Data Preparation

Data management procedures, including database design, selection of the data dictionary, and coding of all adverse events and medications, will be performed by Statistics & Data Corporation (SDC). All reported study data will be recorded on the electronic Case Report Forms (eCRFs) supplied by SDC using iMedNet™ v1.163.3 or higher. Clinical personnel at the study center and Ora, Inc. are responsible for ensuring that the protocol is followed and that the eCRFs are properly completed.

After data are entered into the clinical study database, electronic edit checks will be performed, including checks for missing data, out of range values, discrepancies within and across visits, and cross checks between different data tables. All data validation specifications and procedures are detailed in the Data Validation Manual (DVM). When the database has been declared to be complete and accurate, the database will be locked and treatment codes unmasked. Any changes to the database after that time can only be made with the approval of the Sponsor in consultation with Ora, Inc. and SDC.

All analyses outlined in this document will be performed after:

- All data management requirements are met according to SDC's Standard Operating Procedures (SOPs), including performance of edit and validation checks, documentation and resolution of

- data queries, and database lock with written authorization provided by appropriate SDC and Ora/Sponsor personnel;
- All protocol deviations have been classified as major or minor and the Per Protocol population has been determined; and
 - The treatment codes have been unmasked.

8. Analysis Populations

8.1 Intent-to-Treat

The Intent-to-Treat (ITT) population consists of [REDACTED] All data will be included and no subjects will be excluded because of protocol violations. The ITT population will be analyzed as [REDACTED]

8.2 Per Protocol

The Per Protocol (PP) population is a [REDACTED] [REDACTED]. This population will be analyzed as [REDACTED].

8.3 Safety

The safety population includes [REDACTED]. The safety population will be analyzed as [REDACTED]. No data will be excluded for any reason.

9. General Statistical Considerations

9.1 Unit of Analysis

The subject will be considered the unit of analysis for all efficacy variables. [REDACTED]
[REDACTED]
[REDACTED]
[REDACTED]
[REDACTED]

9.2 Missing or Inconclusive Data Handling

Multiple imputation Markov Chain Monte Carlo (MCMC) methods will be employed to impute missing primary efficacy data. A separate model will be fit for each endpoint, visit and time point. The model will include variables for treatment, baseline measure and response measure.

Sensitivity analyses will be performed as described in the following text:

- ITT Population: [REDACTED]
[REDACTED]
[REDACTED]
[REDACTED]
[REDACTED]
[REDACTED]
[REDACTED]
[REDACTED]
[REDACTED]
- ITT population: [REDACTED].
- PP population: [REDACTED]

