# 10.2.2 Escape Medications

Cold compress should first be used in the management of allergic symptoms. Subjects may be prescribed an anti-inflammatory or anti-allergy medication at the Investigator's discretion. Subjects, however, will be discontinued if prescribed such anti-inflammatory or anti-allergy medication.

Currently marketed over-the-counter anti-allergy eye drops (i.e., anti-histamine/vasoconstrictor combination products such as Visine®-A®) may be administered to subjects at the end of the subject's last visit, after all evaluations are completed.

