3.2 Secondary Variables

The following secondary efficacy assessments will occur pre-CAC and at [REDACTED]

[REDACTED] post-CAC [REDACTED] at Visits 5b and 6:

- Ciliary redness evaluated by the investigator
- Episcleral redness evaluated by the investigator
- Chemosis evaluated by the investigator
- Eyelid swelling evaluated by the subject
- Tearing evaluated by the subject
- Rhinorrhea, nasal pruritus, ear or palate pruritus, and nasal congestion evaluated by the subject
- A composite score of presence or absence of at least one nasal symptom evaluated by the subject

All assessments will be evaluated at pre-CAC and [REDACTED] minutes post-CAC at Visits 4a, 4b, and 5a.

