3.3 Exploratory Variables

The exploratory efficacy variables include the following:

- Conjunctival Inflammation Score (CIS) evaluated by a masked clinician using confocal microscopy post-CAC [REDACTED] Visit 6 (subset of [REDACTED] subjects at one center).
 - Diary assessments for all subjects. Assessments of ocular itching, ocular redness, and eyelid swelling will occur prior to bedtime and upon awakening from Visit 4b to Visit 6 ([REDACTED])

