14.1 Primary Analysis

The primary efficacy endpoints are ocular itching assessed at all time points [REDACTED] [REDACTED] and conjunctival redness assessed at all time points [REDACTED] [REDACTED] at Visit 5b and Visit 6. [REDACTED] [REDACTED]. Ocular itching and conjunctival redness will each be analyzed using an [REDACTED] [REDACTED] [REDACTED] Least squares means (LS Means) for each treatment, LS Means treatment differences, and 95% confidence intervals (CIs) for the LS Means treatment differences will be provided.

Multiple imputation employing the MCMC method will be performed for the primary analysis of the primary endpoints using the SAS procedure PROC MI by applying the following SAS code:

[REDACTED]

where

[REDACTED]

After obtaining twenty complete data sets, the following SAS code will be employed to run the model on each data set:

[REDACTED]

where

[REDACTED]

Then, the following SAS code will be used to analyze the combined data:

[REDACTED]

The primary efficacy analyses will be conducted on the ITT population using MCMC multiple imputation methodology for missing data, as described in Section 9.2 and above. Adjustments for multiplicity will not be employed in this exploratory Phase 2 study.

Sensitivity or supportive analyses will be performed on the ITT population, using LOCF and observed data only, as well as on the PP population with observed data only.

Two-sample *t*-tests will be used as additional sensitivity analyses at each post-CAC® time point, as well as non-parametric Wilcoxon rank sum tests for comparing ST266 ophthalmic drops and placebo. Mean treatment differences, 95% CIs for each of the means, and 95% CIs for the mean differences will be presented.

In addition, ANCOVA models will be run separately at Visit 5b and Visit 6 as secondary analyses, with treatment, time point, and time appropriate baseline as covariates for adjustment (accounting for repeated measurements). LS Means for each treatment, the LS Means treatment difference between ST266 ophthalmic drops and placebo, and the corresponding 95% CIs will be calculated from these ANCOVA models. SAS pseudo-code for the ANCOVA model accounting for repeated measures at each Visit follows:

[REDACTED]

An unstructured variance-covariance matrix will be used for the above repeated measures model. If the model does not converge using the unstructured matrix, the first order autoregressive structure and the compound symmetry structure will be employed, in that order.

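### The primary imputation model leaves out the on-treatment challenge scores already collected; a small shift toward no effect is possible, and the remedy is cheap

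*SAP*

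**What the plan says.** SAP 9.2 imputes missing primary efficacy data by MCMC multiple imputation. On scope it says: "A separate model will be fit for each endpoint, visit and time point". On content it says: "The model will include variables for treatment, baseline measure and response measure". SAP 9.3 sets baseline as the last valid assessment before randomization, generally Visit 3. SAP 14.1 makes this imputation, on the ITT population with twenty completed data sets, the primary analysis of both primary endpoints. The PROC MI code and the name of the primary model are redacted.

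Other scores are available. SAP 3.2 has all assessments made before challenge and "minutes post-CAC at Visits 4a, 4b, and 5a". For the diary, SAP 3.3 says: "Assessments of ocular itching, ocular redness, and eyelid swelling will occur prior to bedtime and upon awakening from Visit 4b to Visit 6".

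The other visible analyses in SAP 14.1 are these: "Sensitivity or supportive analyses will be performed on the ITT population, using LOCF and observed data only"; a per-protocol analysis of observed data; t-tests and Wilcoxon tests at each time point; and repeated-measures models, of which it says "ANCOVA models will be run separately at Visit 5b and Visit 6 as secondary analyses".

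On loss, Protocol 10.2.2 puts cold compress first and leaves prescribing to the investigator. It then states: "Subjects, however, will be discontinued if prescribed such anti-inflammatory or anti-allergy medication". Protocol 10.4.1 has the remaining assessments captured at the visit of discontinuation, but under 10.4.2 the pages for later missed visits are skipped.

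**The concern.** A subject who leaves after Visit 4a, 4b or 5a because of troublesome symptoms has recorded on-treatment scores but no Visit 5b or 6 score. A model with only treatment and the pre-randomization baseline cannot tell that subject from a quiet completer in the same arm. It fills the gap with a typical value for the arm. If the primary model adjusts for treatment and baseline (assumed, since it is redacted), the result is essentially the complete-case answer, and the observed-data analysis then hardly tests the primary one.

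The repeated-measures models do not help, because each stays within one visit. Among the visible analyses only LOCF may draw on earlier scores, and its details are redacted.

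If the drug works, such losses would be expected mainly on placebo. Removing high placebo scores makes the placebo arm look better and shrinks the difference. Protocol 8.1.3 judges success against margins of 0.5 and 1 unit, so a shift would matter mainly for an estimate close to one of them.

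**Working it through.** The documents state no SD, loss rate or power figure (SAP 6 says no data were available for a power calculation), so there is no plan figure to reproduce. Everything below is conditional on assumptions.

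**Assumed inputs.** SD 0.9 unit. True benefit 0.5 or 1.0. Correlation between on-treatment scores / with baseline of 0.7/0.5 or 0.5/0.4. A subject is lost after Visit 4a, 4b, 5a or 5b when score plus noise (SD 0.9) passes a threshold, set to give the stated placebo loss; the same threshold applies on drug. Analysis by ANCOVA on treatment and baseline. Equal arms: 70 / 2 = 35. Then 3% is 0.03 × 35 ≈ 1 placebo subject, and 10% is 3.5.

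**Formula.** In an arm with loss fraction p, let g be the mean score of lost minus retained subjects, at equal baseline. The planned model understates the arm mean by p × g, so the benefit shrinks by p(placebo) × g(placebo) − p(drug) × g(drug). With little loss on drug, 0.03 × 0.3 = 0.009 and 0.10 × 0.6 = 0.06 give the order of size.

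**Large-sample simulation, Visit 6, shift toward no effect (units):**

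| Benefit | Correlations | 3% placebo loss | 10% placebo loss |
|---|---|---|---|
| 0.5 | 0.5/0.4 | 0.011 | 0.028 |
| 0.5 | 0.7/0.5 | 0.015 | 0.037 |
| 1.0 | 0.5/0.4 | 0.016 | 0.043 |
| 1.0 | 0.7/0.5 | 0.021 | 0.056 |

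Loss on drug in these runs is 0.3% to 4%. At 5% placebo loss the range is 0.017 to 0.032. For Visit 5b it is 0.009 to 0.016 at 3% and 0.022 to 0.044 at 10%. With equal loss, or no drug effect, the shift is below 0.001.

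**Scale.** The standard error at 35 per arm is 0.9 × √(2/35) × √(1 − 0.5²) = 0.186, or 0.197 with baseline correlation 0.4; call it 0.19. Then 0.011/0.19 = 0.06, 0.021/0.19 = 0.11 and 0.056/0.19 = 0.29 of a standard error.

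**Wider assumptions.** A second calculation used logistic loss on the preceding score, SD 0.7 to 1.0, correlation 0.6 to 0.8 with that score and 0.3 to 0.5 with baseline. At log-odds 1.0 per SD it gives 0.006 to 0.019 at 3% and 0.020 to 0.062 at 10%. At log-odds 0.5 per SD it goes down to 0.003. Losing exactly the top scorers, a rule the protocol does not have, gives up to 0.136.

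**What the added scores repair (Visit 6):**

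- Recorded scores drive the loss: 0.001 or less remains. This follows from how the case is built.
- Unrecorded symptoms between visits drive it: 0.011–0.021 falls to 0.004–0.006 at 3%, and 0.029–0.055 to 0.010–0.018 at 10%, a cut of about 55–75%.
- Half the loss falls before Visit 4a (benefit 1.0, correlations 0.7/0.5): 0.021 falls to about 0.010, and 0.056 to 0.025. The cut is 0.031/0.056 = 55% in the second case.
- Five-sevenths falls before Visit 4a: 0.020 falls to 0.013 and 0.053 to 0.033. The cut is 0.007/0.020 = 35% in the first case.

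**LOCF in the same runs.** When recorded scores drive the loss, it overstates the benefit by 0.010–0.023 at 3% and 0.024–0.061 at 10%. When between-visit symptoms drive it, it is about unbiased.

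**The case against.** The strongest reply is that the size rests on no document figure. Loss rate, imbalance by arm, dependence on scores, SD and correlations are all assumed. That stands, and it is why the low-loss figure leads: Visits 4a to 6 cover only Days 6 to 8, so low loss is more plausible than 10%.

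The route to score-related loss is also indirect. Enrolled subjects have been selected for a strong challenge reaction, cold compress comes first, prescribing is discretionary, and no passage ties a challenge score to discontinuation. This stands as a reason for calling the loss possible, not expected.

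Next, LOCF is already planned. In one assumed case it errs in the opposite direction to the planned imputation, so the two bracket the truth; in another it does better than the added scores. That also stands. But nobody will know which case applies, and LOCF is not the primary analysis. A gap between LOCF and observed-data results gives warning but no corrected estimate.

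Finally, the redacted code could contain more variables. It could, but the visible list of variables and the one-model-per-time-point rule give no sign of it.

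A reader might infer that the omission could produce a false claim of efficacy, or that it threatens the trial. Neither is supported: the shift is toward no effect, vanishes without a drug effect, and is well below sampling error in a study that the SAP calls exploratory.

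**Conclusion.** The point holds as a minor one. The written primary imputation model ignores relevant scores that the trial collects, and no visible analysis corrects for this. If symptom-related loss is more frequent on placebo, the Visit 6 difference shrinks by about 0.01 to 0.02 unit at 3% placebo loss and about 0.03 to 0.06 at 10%, under the assumptions above; wider ones give about 0.003 to 0.14. In the main scenarios that is at most about 0.3 of a standard error.

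Two stronger readings should be avoided. One is that adding the scores restores the full-data answer. That is true only if the recorded scores drive the loss, and Protocol 10.2.2 does not confine escape medication to Days 6 to 8. Five at-home days precede Visit 4a, and a subject lost then has none of the scores that would be added. The other is that the omission lowers the chance of trial success by some definite amount. Any such figure depends on how close the true benefit lies to the 0.5- and 1-unit margins, and the documents give no expected benefit.

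**What to change.** Before unmasking, amend SAP 9.2 and 14.1 so that each imputation model contains:

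- treatment, the matching Visit 3 baseline and the response, as now;
- one post-challenge score for the same endpoint from each of Visits 4a, 4b and 5a;
- the matching Visit 5b score when Visit 6 is imputed.

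Keep the LOCF and observed-data analyses, and read a gap between them as a warning of symptom-related loss. Report discontinuations linked to escape medication by arm. The disposition reasons in SAP 10 have no such category, but Protocol 10.2 and 10.6.2 already collect the medication, its reason and the reason for discontinuation. Diary scores, site and a joint model of all time points need not be added.

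The cost is a few lines of text and three or four more variables per model, taking one score per visit because the interim post-challenge times are redacted. It needs no new data and no extra subjects. Precision is practically unchanged: at 35 per arm the simulated SD of the estimate, with and without the added scores, stayed within 0.189–0.190 at 3% loss and 0.191–0.193 at 10%. The change does nothing for subjects lost before Visit 4a and only partly repairs loss driven by unrecorded symptoms.

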9.3 Definition of Baseline

For each parameter, the last valid assessment before randomization will be used as the baseline for all analyses of that parameter. For each efficacy variable, the last valid assessment before randomization will generally be at Visit 3.

9.4 Data Analysis Conventions

All data analysis will be performed by SDC after the study is completed and the database has been locked and released for unmasking. Statistical programming and analyses will be performed using SAS® Version 9.4.

Quantitative variables will be summarized using descriptive statistics including the number of observations (n), mean, standard deviation (SD), median, minimum, and maximum values. For the ocular primary and secondary endpoints (itching, eyelid swelling, tearing, regional redness, and chemosis) the unit of analysis is the average of the subject's eyes. Therefore, for each of these variables, the minimum and maximum values will be reported to one decimal, irrespective of the number of decimals in the raw collected data. Similarly, means, medians, and confidence intervals will be reported to two decimal places and standard deviations to three. Summaries for discrete variables will include frequency counts and percentages. All percentages will be rounded to one decimal place (i.e., XX.X%). Differences between the active treatment group and placebo will be calculated as Active minus Placebo and change from baseline will be calculated as follow-up visit - baseline.

All statistical tests will be two-sided with a significance level of [REDACTED] unless otherwise specified.

Confidence intervals (CI) for differences between treatment groups will be [REDACTED]

All p-values will be rounded to four decimal places; p-values less than 0.0001 will be presented as "<0.0001"; p-values greater than 0.9999 will be presented as ">0.9999".

Unless otherwise specified, summaries will be presented by treatment group and, where appropriate, visit and time point.

9.5 Adjustments for Multiplicity

Adjustments for multiplicity will not be employed in this exploratory Phase 2 study.

10. Disposition of Subjects

Subject disposition will be presented in terms of the numbers and percentages of subjects who were randomized, completed the study, and discontinued from the study. Subjects who are not discontinued from the study will be considered study completers. Disposition will be summarized by treatment group and for all subjects.

The number and percentage of subjects prematurely discontinued from the study and the reasons for study discontinuation will be summarized by treatment group for all randomized subjects. The reasons for study discontinuation that will be summarized include: adverse events, protocol violations, lost to follow up, consent withdrawn, sponsor termination of study, investigator decision, screen failure, and other. A subject listing will be provided that includes the date of and reason for premature study discontinuation.

The number and percentage of subjects with protocol deviations will be summarized by treatment group for all randomized subjects. A subject listing will be provided that includes the date of the deviation, the deviation description and the classification of whether the deviation was judged to be major or minor.

In addition, subject listings will be provided that include informed consent date, inclusion and exclusion criteria violations, and exclusions from the PP population.

11. Demographic and Baseline Variables

11.1 Demographic Variables

The demographic variables collected in this study include age, sex, race, ethnicity and iris color. Subjects who record more than one race will be grouped into a single category denoted as multi-racial. Demographic variables will be summarized for the ITT and Safety populations, separately.

Age (years) will be summarized, overall and by treatment, using continuous descriptive statistics. Age will also be categorized as follows: <65 years and ≥ 65 years. Age will be reported in years and calculated using the following formula:

The number and percentage of subjects will be presented, overall and by treatment, for age category, sex, race, ethnicity and iris color. Percentages will be based on the total number of subjects in each

treatment group except for iris color, which will be based on the total number of eyes in each treatment group. A subject listing that includes all demographic variables will be provided.

11.2 Baseline Variables

The number and percentage of subjects with Visit 3 post-CAC® (baseline) itching scores [REDACTED] [REDACTED] will be summarized. A subject listing that includes baseline itching will be provided.

12. Medical History and Concomitant Medications

12.1 Medical History

Medical history will be summarized using discrete summary statistics and presented by treatment group at the subject and event level by system organ class (SOC) and preferred term (PT). If a subject reports the same PT multiple times within the same SOC, that PT will only be reported once within that SOC. As with the PT, if a subject reports multiple conditions within the same SOC, then that SOC will only be reported once. Separate tables will be created for ocular and non-ocular medical history. Medical history will be coded using the Medical Dictionary for Regulatory Activities (MedDRA), version 19.1. The summaries will be based on the ITT population.

Listings of medical history will be generated separately for ocular and non-ocular data.

